Additional outcomes: hospital lengths of stay; time from study drug initiation to maximum allowable ambulation per injury pattern; post-discharge opioid type and dosage provided at the time hospital discharge prescription; and patient report of chronic pain syndromes. Adverse effects including the incidence of hypertension requiring antihypertensive pharmacotherapy in addition to the patients home regimen, hypotension (SBP < 90 mmHg) requiring fluid bolus/vasoactive pharmacotherapy, tachycardia requiring pharmacologic intervention (defined as HR greater than 100 bpm), bradycardia (defined as HR below 60 beats per minute with symptoms or hypotension), respiratory depression (apnea; transition to higher level of respiratory support), emesis, hallucinatory reactions or experiences per patient interview, and pruritus per physical exam.

The study will be stopped if ≥2 patients receiving the active study drug develop the same Grade 3 adverse reaction (Adverse Event Severity

Definition defined previously) or if one patient develops a Grade 4 or higher adverse reaction.

13) Data and Specimen Banking

Not applicable.

14) Data Management and Confidentiality

Each patient will be assigned a unique study ID number at the time of study entry. Study information stored by the research personnel at UCDMC, which may include name and medical record number, will be kept strictly confidential and available only to the principal investigator and trained staff assigned to this study. All information will be kept secure in locked file cabinets accessible only by research personnel. All identifiers for recruitment purposes will be destroyed within 2 years of completion of study.

Statistical Analysis

Data will be presented as means \pm standard errors of the mean (primary endpoint) and proportions \pm interquartile ranges (secondary endpoint). Following assessment for normality, primary endpoint data will either be subjected to parametric unpaired two-sided t-tests or nonparametric Wilcoxon rank sum test Mann-Whitney two sample statistic. Significance will be set at $p = 0.05$. Secondary endpoint proportions will be assessed using either nonparametric chi-square tests or Fisher's exact test.

Other data such as ICU and hospital lengths of stay and adverse events will be collected, summarized, and described. Exploratory analyses these data may be attempted, but these will be hypothesis generating, given the small sample size used in this pilot study.

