Probable/ Likely	
• Event or laboratory test abnormality, with reasonable time relationship to drug intake• Unlikely to be attributed to disease or other drugs• Response to withdrawal clinically reasonable• Rechallenge not required
Possible	
• Event or laboratory test abnormality, with reasonable time relationship to drug intake• Could also be explained by disease or other drugs• Information on drug withdrawal may be lacking or unclear

Unlikely	
 Event or laboratory test abnormality, with a time to drug intake that makes a relationship improbable (but not impossible) Disease or other drugs provide plausible explanations
Conditional/ Unclassified	
 Event or laboratory test abnormality More data for proper assessment needed, or Additional data under examination
Unassessable/ Unclassifiable	
 Report suggesting an adverse reaction Cannot be judged because information is insufficient or contradictory Data cannot be supplemented or verified

The severity of the any potential reaction will be grade using the FDA's guidance for industry. They have been modified to meet the study characteristics and are listed below.

ADVERSE EVENT SEVERITY DEFINITIONS

Vital Signs *	Mild (Grade 1)	Moderate(Grade 2)	Severe (Grade 3)	Potentially Life Threatening (Grade 4)
Dysrhythmia	Unsustained sinus or atrial rhythm < 10 seconds	Unsustained ventricular rhythm <10 secs in duration or sustained sinus rhythms that are asymptomatic	Any rhythm requiring treatment or a change in patient level of care	A ventricular rhythm >10 secs, requiring CPR, cardiac arrest, or any rhythm requiring continuous intravenous therapy
Fever (°C) ** (°F) **	38.0 – 38.4 100.4 – 101.1	38.5 – 38.9 101.2 – 102.0	39.0 – 40 102.1 – 104	> 40 > 104
Tachycardia - beats per minute	101 – 115	116 – 130	> 130	ER visit or hospitalization for arrhythmia
Bradycardia - beats per minute***	50 – 54	45 – 49	< 45	ER visit or hospitalization for arrhythmia
Hypertension (systolic) - mm Hg	141 – 150	151 – 155	> 155	ER visit or hospitalization for malignant hypertension
Hypertension (diastolic) - mm Hg	91 – 95	96 – 100	> 100	ER visit or hospitalization for malignant hypertension
Hypotension (systolic) – mm Hg	85 – 89	80 – 84	< 80	ER visit or hospitalization for hypotensive shock
Respiratory Rate – breaths per minute	17 – 20	21 – 25	> 25	Intubation

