* Subject should be at rest for all vital sign measurements.

** Oral temperature; no recent hot or cold beverages or smoking.

*** When resting heart rate is between 60 – 100 beats per minute. Use clinical judgement when characterizing bradycardia among some healthy subject populations, for example, conditioned athletes.

Systemic (General)	Mild (Grade 1)	Moderate(Grade 2)	Severe (Grade 3)	Potentially Life Threatening (Grade 4)
Nausea/vomiting	No interference with activity or 1 – 2 episodes/24 hours	Some interference with activity or > 2 episodes/24 hours	Prevents daily activity, requires outpatient IV hydration	ER visit or hospitalization for hypotensive shock
Dizziness	No interference with activity or 1 – 2 episodes/24 hours	Some interference with activity or > 2 episodes/24 hours	Prevents daily activity, requires outpatient IV medication	Persistent or associated with a mechanical fall.
Diarrhea	2 – 3 loose stools or < 400 gms/24 hours	4 – 5 stools or 400 – 800 gms/24 hours	6 or more watery stools or > 800gms/24 hours or requires outpatient IV hydration	ER visit or hospitalization
Constipation	Dry, hard, painful stool.	No bowel movement for 48 hours	Requiring rectal suppository or enemas.	ER visit or hospitalization Requiring digital dissimpaction , colonic perforation.
Headache	No interference with activity	Repeated use of non-narcotic pain reliever > 24 hours or some interference with activity	Significant; any use of narcotic pain reliever or prevents daily activity	ER visit or hospitalization
Fatigue	No interference with activity	Some interference with activity	Significant; prevents daily activity	ER visit or hospitalization
Myalgia	No interference with activity	Some interference with activity	Significant; prevents daily activity	ER visit or hospitalization
Methemoglobinemia	Less than 15%; mostly asymptomatic, cyanosis	15% or greater; cyanosis, lightheadedness, headache, tachycardia, fatigue, dyspnea, or lethargy	30% or greater; respiratory depression, altered sensorium, coma, shock, seizures	70% or greater; severe hypoxia, cardiac arrest

16) Withdrawal of Subjects

a) **Stopping Criteria** – This study involves a single dose medication; therefore, individual stopping criteria will not be related to the continued administration of study drug, but rather ability of the subject to continue to

participate in the follow-up evaluations. The following clinical situations and the methods of follow-up to deal with them are as follows:

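### One Grade 4 reaction stops the study, and dizziness that is merely persistent, however mild, meets Grade 4

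*Combined protocol and SAP*

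**What the plan says.** The stopping rule stands at the end of the outcome definitions in section 12 (Procedures Involved). It has two limbs. The study stops if at least two "patients receiving the active study drug develop the same Grade 3 adverse reaction", or "if one patient develops a Grade 4 or higher adverse reaction". It is worded as a requirement and refers to the protocol's adverse event severity definitions.

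Those definitions are in section 15. They start from an FDA grading scale, and the protocol says of them: "They have been modified to meet the study characteristics and are listed below". The fourth column is headed "Potentially Life Threatening (Grade 4". The dizziness row reads:

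- Grade 1: "No interference with activity or 1 – 2 episodes/24 hours"
- Grade 2: "Some interference with activity or > 2 episodes/24 hours"
- Grade 3: "Prevents daily activity, requires outpatient IV medication"
- Grade 4: "Persistent or associated with a mechanical fall"

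Section 17 lists dizziness, with no severity stated, as a reaction to both drugs: 2% to under 10% for liposomal bupivacaine and 1 to 5% for ropivacaine. Section 7 sets 17 patients per arm, 34 in total.

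**The concern.** Grades 1 to 3 of the dizziness row each depend on interference with activity, number of episodes or need for treatment. Grade 4 drops all of these. Because its two conditions are joined by *or*, dizziness that simply lasts is enough, and nothing says how long or how bad it must be.

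Only one Grade 4 reaction is needed to stop the study, so this cell works as a one-patient stopping trigger. Followed as written, a reaction that threatens nobody's life could end the trial before the primary comparison of 96-hour opioid use can be made. If the same reaction were Grade 3, it would have to occur in two active-arm patients.

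**Working it through.** **Reading the row**

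1. Take a patient whose dizziness persists but interferes with nothing. The first condition of Grade 1 is met. The first condition of Grade 4 is also met.
2. Take a patient whose dizziness prevents daily activity but is not persistent and involves no fall. This is Grade 3 at most.
3. The milder case can therefore be graded above the worse one, and it falls in two grades at once.

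The other Grade 4 cells differ. They call for an emergency visit or hospitalization, a treatment such as intubation, a measured limit, a dangerous rhythm, or a plainly grave condition such as colonic perforation or severe hypoxia. Dizziness is the only row whose Grade 4 cell a possibly trivial symptom can meet by itself.

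**Size**

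The plan states no operating characteristic for the stopping rule, so there is no figure to reproduce. Let *p* be the chance that a patient has persistent dizziness judged to be a reaction. It is assumed, because the documents do not give it. Patients are taken as independent, with a constant rate and full enrolment unless the rule stops the trial.

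- Stop from this cell at Grade 4: 1 − (1 − p)^n, with n = 34 if both arms count and n = 17 if only the active arm counts.
- Stop if graded 3: P(X ≥ 2), X ~ Binomial(17, p), because that limb is restricted to the active arm.

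| Assumed p | Grade 4, n = 34 | Grade 4, n = 17 | Graded 3 |
|---|---|---|---|
| 0.1% | 3.3% | 1.7% | about 0.01% |
| 0.5% | 15.7% | 8.2% | 0.3% |
| 1% | 28.9% | 15.7% | 1.2% |
| 2% | 49.7% | 29.1% | 4.5% |

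Example at p = 1%: 1 − 0.99^34 = 0.289 and 1 − 0.99^17 = 0.157.

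A check against the listed rates: suppose 10% of all dizziness is persistent (also an assumption). The per-patient rates are then 0.2% to 1% on liposomal bupivacaine and 0.1% to 0.5% on ropivacaine. The chance of a stop is 1 − (1 − p_L)^17 (1 − p_R)^17 = 5.0% to 22.6% if both arms count, and 3.3% to 15.7% for the active arm alone.

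**Allowing for the rest of the rule**

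If everything else in the rule would stop the trial with chance *q*, independently, the net addition from this cell is (P4 − P3)(1 − q), where P4 and P3 are the chances above.

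Grade 3 constipation shows that *q* may be large. It is met by needing a suppository or an enema, and constipation of any severity is listed at 10% or more for liposomal bupivacaine. At an assumed 10% rate of Grade 3 constipation, the chance of two or more cases among 17 is 1 − 0.9^17 − 17(0.1)(0.9^16) = 1 − 0.167 − 0.315 = 0.518.

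Net addition at p = 1%, where P4 − P3 = 0.289 − 0.012 = 0.277 (n = 34) or 0.157 − 0.012 = 0.145 (n = 17):

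| Assumed Grade 3 constipation rate | q | Net, n = 34 | Net, n = 17 |
|---|---|---|---|
| none | 0 | 28 points | 14 points |
| 10% | 52% | 13 points | 7 points |
| 15% | 75% | 7 points | 4 points |
| 20% | 88% | 3 points | 2 points |

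**The case against.** The best defence is that no sensible grader would apply the cell this way. The column is for potentially life-threatening events, the grades rise from left to right, and Grade 4 could be meant as Grade 3 dizziness that does not resolve. The scale was adapted on purpose, and the fall wording suits these patients. A sensitive rule is also reasonable in a pilot of a drug that, by the protocol's account, has not been studied in trauma patients.

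Part of this stands. A low threshold for stopping is a legitimate choice, and investigators may well read the cell sensibly. But the heading does not change the condition in the cell, and the documents as available give nobody discretion over the stop. Nor does the protocol treat dizziness as a sign of anesthetic toxicity: the central nervous system signs for unblinding in section 16 are paresthesia, acute anxiety, tinnitus and seizure.

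The objection to the size also stands. The rate is assumed. The 50% figure needs 2% persistent dizziness in both arms, which equals all listed liposomal dizziness at its lower bound and twice the lower bound for ropivacaine. As shown above, other cells may leave only a few points of net effect.

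A reader might infer three stronger points that the text does not support:

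- *That dizziness is the only row whose Grade 4 cell needs no care event, measured limit or dangerous rhythm.* Colonic perforation, in the constipation row, is none of these. What sets dizziness apart is that its cell need not describe anything dangerous.
- *That the arm covered by the Grade 4 limb is an error.* It says one patient, and the Grade 3 limb shows that the authors wrote an arm restriction when they wanted one. The natural reading is either arm.
- *That the rule ignores causality.* It already speaks of an adverse reaction, and section 15 carries the WHO-UMC scale. Not naming a category is missing detail.

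**Conclusion.** The point holds as a defect in one table cell that feeds a mandatory stop. It rests on the wording and needs no event rate: bare persistence is sufficient for Grade 4, the dizziness row does not order severity, and one reaction that is not dangerous could stop the trial.

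The size is uncertain. Over assumed rates of 0.1% to 2%, the cell alone stops the trial with chance 3% to 50% if both arms count, the more natural reading, or 2% to 29% for the active arm alone. Graded 3, the range is about 0% to 4.5%. These figures assume independent patients and a constant rate, and they overstate the net effect to the extent that other cells would stop the trial anyway. They should not be read as a forecast that the trial will stop. Nor do they show a biased primary endpoint: what is at risk is information.

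**What to change.** In the dizziness row of the severity table (section 15), remove bare persistence from Grade 4. Either move it to Grade 3 or lower, or require that the persistent dizziness be life-threatening. Keep dizziness associated with a mechanical fall as a Grade 4 trigger. All other Grade 4 triggers are unaffected.

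The cost is one table cell and a protocol amendment. The downside is a slightly less sensitive stopping rule.

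Optionally, the same amendment could add to the stopping rule in section 12 that Grade 4 reactions in either arm count, if that is the intention, and name the lowest WHO-UMC category that qualifies, for example *Possible*. This is a clarification and not part of the error.

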- 14) Pediatric patients <18 years old
- 15) Patients exhibiting signs of shock upon admission, HR >120 or SBP <100 mmHg.
- 16) History of allergic reaction to local anesthetics
- 17) Administration of any other local anesthetic in the 2 hours prior to the study enrollment.
- 18) Distal femur fractures

7) Number of Subjects

17 patients per arm

Total subjects: 34

8) Recruitment Methods

Subjects will be recruited from the UC Davis Trauma Center. Patients found to have femur and /or hip fractures admitted to UCDMC will be screened for eligibility.

Waiver of HIPAA authorization for recruitment is requested for access to PHI during the screening to determine eligibility.

Description of PHI that will be accessed.

Information reviewed to assess eligibility will include: date of admission, date of birth, gender, mechanism of trauma injury (blunt/penetrating), x-rays, lab results, admission vital signs, home medications and the patient's medical history.

The use of PHI involves no more than minimal risk and granting of waiver will not adversely affect privacy of the patients.

Access to medical records that contain patient's personal information for the purpose of this study will be limited to the approved research personnel. These personnel already have knowledge of and access to identifiable medical information of current trauma patients as part of their daily job functions; hence, granting of this waiver will not adversely affect the privacy of the involved patients or the confidentiality of their information. EMR access to PHI is password-protected and no PHI will be reused or disclosed to any

other person or entity, except as required by law. Data will be used solely for the purposes of determining study eligibility.

The research could not practicably be conducted without a waiver or alteration.

Without an initial review of the medical record for screening purposes, it would not be possible to identify potential subjects and confirm their applicability for study participation.

The research could not practicably be conducted without access to and use of PHI.

Since PHI is embedded in the medical record and since the screening process requires detailed information about trauma patients, access to medical records (viewing of PHI) is necessary.

9) Compensation to the Subjects

Subjects will not be compensated for this study.

10) Study Timelines

The duration of each subject's participation is the length of their hospital stay.

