Duration anticipated to enroll all study subjects: 12 months.

Data acquisition and analysis: same 12 months

Manuscript preparation: 6 months

Total time requirement: 1.5 years

11) Study Endpoints

Hypothesis: In patients with femur or hip fractures, a fascia iliaca compartment block using liposomal bupivacaine will require less total opioid administration compared to a fascia iliaca block using 0.2% ropivacaine.

Primary Endpoint

(1) Total opioid requirement during the 96 hour randomization period measured in milligram morphine equivalents.

Secondary Endpoint

(1) Percentage of time during the 96 hour randomization period that the objective pain score was above mild (defined as a numeric rating score >4).

12) Procedures Involved

The nature of the risks and benefits associated with participation in the study will be explained to all potential study subjects. Written informed consent must be obtained before the subject can begin any screening procedures that are not considered standard patient care. Subjects who have undergone the screening procedures and have met the entry criteria will be randomized into the study and assigned to treatment by the Unblinded Pharmacist. Subjects will be randomized in a computer-generated, blinded block, 1:1 ratio to treatment with 60mL of either 0.2% ropivacaine (120mg) or a dilution of liposomal bupivacaine (266mg).

The Pharmacy and Emergency Medicine (EM) members will be the only unblinded study team members. All other members, including the Trauma team and Clinical Research Coordinator (CRC), will remain blinded.

The unblinded Investigational Drug Service (IDS) Pharmacy at UC Davis Health (UCDH) will be responsible for blinding and drug preparation. Investigational Product (IP) will be prepared in three 35mL Luer lok syringes, each containing 20mL of IP, for a total dose of 60mL. In addition to a patient-specific institutional label, masking/amber tape will also be affixed to the syringes in order to reduce the risk of drug recognition by a supporting procedure nurse. During the procedure, nursing care of the patient will temporarily transition from the primary bedside nurse to a supporting procedure nurse. The supporting procedure nurse will remain blinded and will assist primarily with assessments and recording of vital signs (but will not work directly with the IP).

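### An unspecified normality check on the outcome data picks the primary test, so the hypothesis tested, and sometimes the verdict, is settled after the data are seen, while only means and standard errors are reported

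*Combined protocol and SAP*

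**What the plan says.** Section 11 defines the primary endpoint as "Total opioid requirement during the 96 hour randomization period measured in milligram morphine equivalents". Section 7 sets the size at "17 patients per arm", and section 12 allocates 1:1 in blocks.

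The Statistical Analysis text, placed under section 14, sets the primary test: "Following assessment for normality, primary endpoint data will either be subjected to parametric unpaired two-sided t-tests or nonparametric Wilcoxon rank sum test". The significance level is 0.05, and two-sidedness is stated for the t-test branch ("parametric unpaired two-sided t-tests"). The primary endpoint is to be shown as means with "standard errors of the mean (primary endpoint"), with no other summary if the Wilcoxon branch is taken.

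The text does not give:
- the normality method or its threshold;
- whether the check is on each arm, on residuals or on pooled data;
- who makes it, and whether arm labels are hidden at that point;
- a default test, or a sensitivity analysis with the test not chosen.

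**The concern.** The trial has one primary comparison, with a directional hypothesis and a 0.05 threshold. Which test delivers it is decided from the outcome data, by a rule that is not written down. Three things follow.

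1. **Room to choose.** Two analysts could both follow the text, reach different tests and, in some data sets, different verdicts.
2. **The question changes with the branch.** The t-test concerns a difference in mean totals. The Wilcoxon test concerns a shift in ranks. A Wilcoxon p-value would be printed beside means it does not test, with no matching estimate or interval.
3. **Skew is plausible.** The total cannot be negative and comes from as-needed dosing (section 12). The documents give no distribution, so skew is an assumption, but it is the setting in which the two tests part company most.

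**Working it through.** **Inputs from the documents.** 17 per arm, 1:1 allocation, two-sided 0.05, unpaired t-test or Wilcoxon. The plan gives no error rate for the two-step procedure, so there is no figure of its own to reproduce.

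**Assumptions.** The distribution of totals; a pooled-variance t-test; an asymptotic Mann-Whitney p-value with continuity correction; and a Shapiro-Wilk check at 0.05, applied per arm (both must pass), to residuals, or to pooled raw data. Each null scenario has 40,000 simulated trials, both arms sharing one distribution. The simulation error near 5% is √(0.05 × 0.95 / 40,000) ≈ 0.11 points.

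**Step 1: type I error (%).** "Either" in the formulas below means that at least one test is significant.

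| Assumed totals | t fixed | Wilcoxon fixed | Trials in t-branch, per-arm check | Error within that branch | Whole procedure: per arm / residual / pooled | Either test significant |
|---|---|---|---|---|---|---|
| Normal | 5.1 | 4.9 | 90 | 5.0 | 5.2 / 5.2 / 5.1 | 6.0 |
| Gamma, CV 0.5 | 5.0 | 4.9 | 57 | 5.9 | 5.6 / 5.5 / 4.9 | 6.1 |
| Gamma, CV 0.71 | 4.7 | 4.6 | 31 | 7.1 | 5.3 / 5.3 / 4.6 | 6.0 |
| Lognormal, log-SD 0.5 | 4.6 | 4.8 | 31 | 7.0 | 5.4 / 5.4 / 4.9 | 6.1 |
| Lognormal, log-SD 0.8 | 4.3 | 5.0 | 6 | 11.6 | 5.2 / 5.3 / 5.0 | 6.5 |
| Exponential | 4.5 | 4.9 | 6 | 11.9 | 5.2 / 5.3 / 4.9 | 6.4 |
| Lognormal, log-SD 1 | 3.8 | 4.7 | 1.5 | 15.1 | 4.8 / 4.8 / 4.7 | 6.2 |

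Within the t-test branch, the residual check gives 5.1% for normal data and 6.4% to 29% for skewed data. The pooled check gives 4.7% to 5.9% wherever the branch is reached in at least 1% of trials.

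**Step 2: why the overall rate stays near 5%.** Overall error = P(t-branch) × error in t-branch + P(Wilcoxon branch) × error in Wilcoxon branch. For log-SD 0.8 with the per-arm check: 0.058 × 0.1164 + 0.942 × 0.0481 = 0.0068 + 0.0453 = 0.052. The inflated branch is rarely reached when skew is strong.

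**Step 3: the open choice.** P(either) = [P(t) + P(Wilcoxon) + P(they disagree)] / 2. For normal data: (0.0505 + 0.0493 + 0.0210) / 2 = 0.0604. For log-SD 1: (0.0379 + 0.0469 + 0.0396) / 2 = 0.0622. Across the table this is 6.0% to 6.5%. Repeat runs put the upper end at about 6.7%, and that of the fixed-rule procedure at about 5.8%.

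**Step 4: verdicts under a true effect (20,000 trials each).**

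| Scenario | t power | Wilcoxon power | Two-step power, per-arm check | t and Wilcoxon disagree |
|---|---|---|---|---|
| Normal, standardized difference 0.96 | 77.8% | 75.0% | 77.6% | 5.9% |
| Lognormal, log-SD 0.8, ratio 0.6 | 34.1% | 41.3% | 41.9% | 16.1% |
| Lognormal, log-SD 0.8, ratio 0.5 | 55.7% | 65.9% | 66.2% | 17.6% |

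The disagreement column compares always-t with always-Wilcoxon. A followed per-arm rule differs from always-Wilcoxon in about 0% to 2% of lognormal trials, and in up to about 6% when totals are near normal.

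**Step 5: the branches test different hypotheses.** Take equal means but unequal spread (lognormal, log-SD 0.8 against 0.4). The t-test rejects in 7.7% of trials and the Wilcoxon test in 19.1%. A significant rank test need not mean that mean opioid use differs.

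**The case against.** The strongest defence is that the two-step rule does little damage. Fixed and followed, it keeps overall error near 5%, and with skewed totals it behaves almost like always using Wilcoxon. The text ties the choice to normality, not to the p-value, and section 12 keeps everyone except pharmacy and emergency medicine members blinded. The trial also calls itself a pilot.

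Most of this stands, and it rules out three stronger readings.

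- *The t-test branch does not hold 5%.* A reader might infer this from the conditional rates of 6% to 29%. It is not general: the branch holds 5% for normal data under all three checks, and about 5% with a pooled check. The documents state neither skew nor a per-arm or residual check.
- *The verdict would change in up to a fifth of trials.* That compares two fixed tests, which the plan does not propose. The planned rule moves far fewer verdicts.
- *The analyst will pick the better p-value, or will check normality unblinded.* The documents say neither. They are silent on who checks and how, so this is possible but not planned.

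The defence does not supply the missing rule. The low error rates belong to rules that the plan does not contain. Nor does pilot status cover the primary test: the remark that "these will be hypothesis generating, given the small sample size used in this pilot study" concerns exploratory analyses of the other data.

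**Conclusion.** The point holds as a specification fault in the primary analysis, not as gross inflation of error. The choice of test, and with it the hypothesis, depends on an unwritten judgement made on the outcome data, and the reported summary matches only one branch. The avoidable excess from an open choice is about 1 to 1.7 points above 5% at worst (6% to 6.7%). It would be about 0.8 points or less under a fixed, followed Shapiro-Wilk rule (at most about 5.8%).

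These figures rest on assumed distributions shared by both arms and on an assumed form of the check. The mismatch between test and reported summary rests on the text alone. It is worth correcting because the correction is cheap and the endpoint is primary.

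**What to change.** Delete the normality step and, before unblinding, name one primary test with its own estimate. For example: the two-sided Wilcoxon rank-sum test at 0.05 on the 96-hour morphine-equivalent total, with an exact or permutation p-value that handles ties (totals built from standard doses may tie), the Hodges-Lehmann shift with its 95% CI, and medians with interquartile ranges as the main summary. Report the t-test with the mean difference only as a labelled sensitivity analysis.

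Wilcoxon is a preference. A pre-named t-test with the mean difference and its CI would also remove the fault, since either test, once fixed, stays at or below about 5% when the arms share a distribution. If a single covariate-adjusted model is adopted instead, it alone should be primary.

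The cost is a sentence on the test and a matching change to the summary statistics. If totals are truly normal, Wilcoxon loses 61.7% − 59.2% = 2.5 points of power at a standardized difference of 0.8. If they are lognormal with log-SD 0.8 and ratio 0.5, it gains 65.9% − 55.7% = 10.2 points over the t-test.

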The patient will be blinded and all members of the healthcare team will be blinded from the point of transfer of care from the Emergency Department physicians to the receiving service.

Both groups will be able to receive as needed analgesia per the primary attending service. (e.g., oral hydrocodone/acetaminophen 5/325 mg or narcotic IV push as needed for breakthrough pain).

Patients enrolled in the study will be given a light blue wristband for identification to alert physicians regarding restrictions for anesthetics. Additionally, an automatic alert notification will be given by the Electronic

Medical Record system if additional local anesthetics are ordered for the patient.

Pain Assessment

Objective pain assessment will be evaluated by the UCDMC nursing staff per local standard of care which is every four hours while the patient is awake using a numeric rating scale (NRS) of 0 to 10 with a pain score of 0 being defined as: no pain, 1-4 mild pain, 5-7 defined as moderate pain, and 8-10 defined as severe pain.

Study Definitions

Acute and hospital-related adverse effects and study outcomes will be collected and tracked prospectively during the FICB and throughout the hospital stay, as appropriate per endpoint.

During hospital stay study outcomes

Data collection will include total amount of opioids administered to study patients in morphine equivalents (see Appendix) and the use of other analgesic medications during this time period. Adjunctive analgesic use including non-steroidal anti-inflammatory drugs, acetaminophen, and gabapentin will be quantified. Use of additional adjunctive agents such as muscle relaxants also will be collected.

All objective pain and agitation scores reported by the NRS will be collected; duration of supplemental oxygen requirement; number of episodes of oxygen desaturation (arterial O₂ sat below 92%); morning incentive spirometer and peak flow measurements; 24-hour antiemetic (e.g., promethazine; ondansetron) pharmacotherapy; time to first bowel movement; and need for anti-hallucination or anti-delirium pharmacotherapy.

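### The primary opioid comparison is valid but unadjusted; pre-specifying one or two baseline covariates is a cheap improvement whose gain depends on how prognostic they are

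*Combined protocol and SAP*

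**What the plan says.** The primary endpoint (Section 11) is total opioid over 96 hours in morphine equivalents. Section 14, Statistical Analysis, gives its test: "Following assessment for normality, primary endpoint data will either be subjected to parametric unpaired two-sided t-tests or nonparametric Wilcoxon rank sum test". The test is two-sided at 0.05. No covariate, stratified analysis or treatment-effect interval is mentioned, and the endpoint is to be summarised by means with standard errors.

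Section 7 sets the size at "17 patients per arm" and "Total subjects: 34", without an effect size, SD or target power. Section 12 describes allocation: "Subjects will be randomized in a computer-generated, blinded block, 1:1 ratio to treatment". No stratification factor is named. The exclusions in Section 6 do not mention prior opioid use, and patients may be enrolled up to 10 hours after reaching the emergency department.

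Three places bear on baseline information:

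- Section 8 lists what is read at screening, including "admission vital signs, home medications and the patient's medical history". It limits those data to deciding eligibility.
- Section 12, under hospital-stay outcomes, says "All objective pain and agitation scores reported by the NRS will be collected".
- The same part of Section 12 collects opioids given, in morphine equivalents.

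No pre-block pain score or pre-block opioid dose is listed as a baseline item.

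**The concern.** Opioid consumption under as-needed analgesia plausibly varies a good deal between patients for reasons fixed before the block, such as regular opioid use at home and opioid already needed in the emergency department. A two-sample test leaves all of that spread in the error term. With 17 per arm and no stratification, a visible imbalance is also quite likely. If 30% of patients used opioids at home (an assumption), the difference in counts between arms has variance 2 × 17 × 0.3 × 0.7 = 7.14, SD 2.67. The arms would then differ by three or more patients in about 35% of trials.

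The plan has no agreed way to account for such an imbalance, and an adjustment chosen after seeing the data would carry little weight. At stake is the precision of a small trial whose stated purpose is to inform larger ones.

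**Working it through.** **Inputs from the documents:** 17 per arm, 1:1 allocation, two-sided 0.05, no covariates.

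**Assumptions, because the documents give no figures:** log-normal morphine equivalents with coefficient of variation 0.75, a true ratio of 0.6, no dropout, and R² (the share of log-scale variance explained by the covariates) from 0 to 0.36. The plan's sample size cannot be reproduced, since no effect size, SD or power accompanies it. Text between Section 24 and the consent section was not available to this review, so a power statement there cannot be ruled out.

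**Step 1, standardised effect on the log scale.** The log SD is √ln(1 + 0.75²) = √0.446 = 0.668. The log effect is |ln 0.6| = 0.511. So d = 0.511 / 0.668 = 0.765, and the noncentrality is 0.765 × √(17/2) = 2.23. On 32 df this gives 58.0% power for an unadjusted log-scale t-test.

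**Step 2, adjusted power.** With k covariates, residual variance is multiplied by (1 − R²). Chance covariate imbalance inflates the variance of the treatment effect by 1 + k/(31 − k). Hence

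noncentrality = 2.23 / √[(1 − R²)(1 + k/(31 − k))], on 32 − k df.

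The inflation factor is 1.033 for k = 1, 1.069 for k = 2 and 1.107 for k = 3.

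| R² | k = 1 | k = 2 | k = 3 |
|---|---|---|---|
| 0 | 56.6% | 55.1% | 53.5% |
| 0.09 | 60.5% | 59.0% | 57.4% |
| 0.20 | 66.1% | 64.5% | 62.9% |
| 0.25 | 68.9% | 67.3% | 65.7% |
| 0.36 | 75.7% | 74.2% | 72.6% |

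Apart from the small change in df, adjustment breaks even where (1 − R²)(1 + k/(31 − k)) = 1, that is at R² = k/31: about 0.03, 0.06 and 0.10 for one, two and three covariates.

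**Step 3, the planned test.** The plan names no normality rule, so the simulation assumed Shapiro–Wilk at 0.05 in each arm. In 8,000 trials per setting:

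- The two-stage test had about 56% power and the unadjusted log-scale t-test about 58%. Roughly 2 points (1 to 2 across runs) therefore come from the log scale alone.
- At R² 0, 0.09, 0.20, 0.25 and 0.36, one covariate gave 56.6, 60.2, 65.9, 68.5 and 76.0%. Two gave 55.2, 59.1, 64.5, 66.7 and 74.5%.
- With no true effect, the planned test rejected in 5.4% of trials and the adjusted models in 4.9 to 5.0%.

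Separate simulations of the same scenario agree within about 1 to 2 points, so the brief gives ranges.

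**The case against.** The strongest reply is that nothing here needs correcting. Randomisation makes the unadjusted comparison unbiased, its error rate already allows for chance imbalance, and the study calls itself a small pilot. That stands: adjustment is an efficiency gain. A reader might infer that the planned test is biased or invalid, and the simulated type I error does not support that.

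A reader might also infer that the trial forfeits a fixed amount of power, say 5 to 19 points. The documents supply none of the quantities needed for such a figure. It fits a single covariate with a correlation of 0.3 to 0.6 under the assumed spread and effect, and its lower end is not a floor. With three covariates at R² 0.09 the net gain over the planned test is only about 1 point, and with uninformative covariates adjustment loses power.

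A third tempting reading is that the baseline values are already trial data. Only home medications are named, and Section 8 restricts those to eligibility. That pre-block scores and doses are charted is a fair inference from the 10-hour window and the Section 12 collection, but the documents do not list them as study variables.

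Finally, a log-scale model changes the summary from a difference in means to a ratio of geometric means. That is a real cost, and it also stands.

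The pilot label does not remove the point: Section 4 states a directional efficacy hypothesis, Section 14 tests it at 0.05, and the results are meant to guide later trials.

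**Conclusion.** The point holds as a cheap improvement to a valid plan. Under the assumed spread and ratio, one or two covariates bring little or nothing over the planned test when uninformative (about +1 to −2 points). The gain is about 3 to 5 points at R² 0.09, 8 to 10 at R² 0.20 and 18 to 20 at R² 0.36, including the 1 to 2 points due to the log scale. Against an unadjusted test on the same scale, useless covariates cost 58.0 − 56.6 = 1.4 points (one) or 58.0 − 55.1 = 2.9 points (two). These sizes rest wholly on assumed values. The direction needs only that the chosen covariates explain more than about 3% (one) or 6% (two) of the log-scale variance. Two further benefits do not depend on R²: a single named analysis, and an effect estimate with an interval, which Section 14 does not now promise.

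**What to change.** In Section 14, make the primary analysis one linear model on log morphine equivalents, using log(MME + 1) if any total is zero. Include treatment and one or two named baseline covariates, for example pre-block opioid dose (on a stated scale, with a cut-off that cannot overlap the 96-hour outcome window) and home opioid use (yes/no). Report the adjusted ratio of geometric means with 95% CI and p-value, and keep the unadjusted Wilcoxon test as a sensitivity analysis. Fix the covariates before any comparison by arm, and hold them to two, since a third uninformative one costs about another 1.6 points (55.1 − 53.5).

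Record the covariates as defined baseline items on the case report form, under the HIPAA authorization signed at consent, because the screening waiver does not extend to analysis.

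The costs are revised wording, a few charted values for each of 34 patients, one or two of 32 degrees of freedom (about 1 to 3 points of power if the covariates are not prognostic), and the change of summary measure. Means by arm can still be shown descriptively.
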